4.2 Screening

Outpatient providers at VUMC will have access to an "IC/BPS Intervention Referral Form" (**Appendix A**) to be completed with interested patients. This form will either be completed on paper, online, or via electronic health record once available. Prior to completing study eligibility questions, participants will undergo brief consenting procedures for eligibility screening where they will be informed of the screening purpose, duration, and that their participation is strictly voluntary. This form assesses for the presence of IC/BPS, current symptoms, and appropriateness for treatment. In the event that screening cannot occur in person, prospective participants will complete screening questions via telephone or online in Redcap. We are requesting a waiver of documentation for this stage of the screening process.

Regarding the telephone screening and contact with interested participants, research team members will follow a script (**Appendix B**) informing patients of the study purpose and inclusion/exclusion criteria. Research assistants will also follow an in-person screening script (**Appendix C**) if recruiting in person. Inclusion/exclusion criteria will follow a structured checklist that prospective participants will complete via these methods or online by answering questions in Redcap.

During recruitment and screening, any participants who indicate that they are having thoughts of self-harm or suicide will be provided with resources for follow-up immediately (i.e. the telephone number to the National Crisis Hotline and website www.suicidepreventionlifeline.org to chat with support staff online, and PI office number). Additionally, the research team member will inform the PI, who will also follow-up with the potential participant within 24-48 hours to assess if further assistance or referrals are necessary in order to provide adequate support. The PI will also provide a direct phone number to call during business hours to be available to participants for additional support and to make any necessary referrals. These participants will not be eligible for study participation.

Those who indicate they are interested in participating in research during screening procedures and meet inclusion criteria will be contacted by the PI or a member of the research team (e.g. research coordinator, post-doctoral fellow, or research assistant) to discuss study procedures, answer any questions, and confirm dates/times of appointments. This will occur via telephone, secure zoom video conferencing software, or in-clinic if a member of the research team is available. Participants will then schedule a time to undergo consenting procedures (separate consents for the intervention study and optional psychophysical testing) and a pre-treatment assessment. At the initial visit, the pre-treatment assessment will involve a series of (1) self-report instruments to assess physical and emotional functioning, and (2) in-person psychophysical measures including pain sensory testing and blood draws (optional). Those who use opioids regularly will be instructed to not use opioids prior to their psychophysical testing, as this could impact its outcome. Those who elect to participate in in-person assessment visits will undergo blood draws to assess for potential inflammatory responses to pain. Participants will also provide urine samples for analysis of the presence of infection. Total time in both stages of this assessment will be approximately 90 minutes - approximately 45 minutes to complete patient-reported outcomes and approximately 45 minutes to complete in-person psychophysical assessments.

4.3 Inclusion criteria

Inclusion and exclusion criteria will be assessed with a structured checklist by the individual screening the participant (**Appendix D**).

1. 18 years of age or older;*
2. Diagnosis of IC/BPS as given by providers or indicated by assessments (RICE screening criteria).

4.4 Exclusion criteria

1. Comorbid neurological conditions including spinal cord injury or systematic neurologic illnesses, or central nervous system diseases such as brain tumor or stroke.
2. Current or history of diagnosis of primary psychotic or major thought disorder within the past five years;
3. Hospitalization for psychiatric reasons other than suicidal ideation, homicidal ideation, and/or PTSD (within the past 5 years);
4. Psychiatric or behavioral conditions in which symptoms are unstable or severe (e.g. current delirium, mania, psychosis, active suicidal ideation, homicidal ideation, substance abuse dependency) reported within the past six months;
5. Non-English speaking
6. Presenting symptoms at time of screening that would interfere with participation, specifically active suicidal ideation with intent to harm oneself or active delusional or psychotic thinking;

7. Difficulties or limitations communicating over the telephone.
8. Any planned life events that would interfere with participating in the key elements of the study.
9. Any major active medical issues that could preclude participation.
10. Currently being treated for cancer.
11. Cancer-related pain.
12. Currently engaged in individual counseling/psychotherapy or unwilling to pause this treatment for the trial duration.

*There will not be an upper age cutoff for study participation because individuals of all ages can be successfully treated, including those over 80 years old.

5. STUDY PROCEDURES

5.1 Overview

Participants will complete a total of three assessments before, immediately after, and 3 months following an 8-week period where they will either receive an 8-week series of psychosocial intervention or attention control visits. This equals a total of 11 visits with VUMC. Based on attrition rates from investigations in similar chronic pain conditions,³⁸ we will assume a conservative study dropout rate of 30%, and will recruit up to 96 participants in order to attain complete data on 75 subjects. In order to recruit 96 participants including follow-up we anticipate this study will occur over the course of three to four years. Below we detail a summary of the visit structure along with a figure indicating study flow.

The assessments corresponding to the study will occur in two stages at each of the three timepoints: (1) completion of patient-reported outcomes online, and optional (2) completion of psychophysical testing and the collection of biological samples in person at the CRC. Participants will have the option of enrolling in the first or both stages of these assessment visits, each of which will have separate consent forms.

Once patients pass the phone screen, they will be scheduled for a Study Enrollment visit, to take place remotely over the phone or online. They will present for a remote assessment visit to complete consenting procedures and will be sent patient-reported outcome measures online via REDCap. Those who elected to participate in in-person psychophysical testing procedures will then be scheduled for the CRC. Patients in the Study Enrollment Visit will complete separate consent forms corresponding to the online and in-person study procedures. The eligibility checklist will be reviewed again to ensure participants meet criteria and assessment battery will be given. Participants who enroll in the study will be randomized after the assessment (see section 5.3 for full description of randomization procedures).

Pretreatment visit (1, T0):

Once patients are screened and determined to be eligible to participate in the study, they will complete informed consent and an assessment battery remotely. If they agree to undergo psychophysical testing, they will be scheduled to do so at the **Clinical Research Center** (CRC) for their first pre-treatment assessment visit (procedures detailed below).

Visits (2-9, T1):

Participants will either receive a series of 8-week psychosocial intervention or attention control visits for an 8-week period at the Osher Center for Integrative Medicine, online, or via telephone. Each of the 8 treatment condition appointments will span 50 minutes.

Post-treatment Visit (10, T2):

Participants will complete a repeat corresponding battery of psychological (stage 1), psychophysical, and biological testing (stage 2) immediately after 8 weeks of visits.

[figure not shown]
3-month Follow-up Visit (11, T3):

Participants will complete a repeat battery of testing to investigate effects at follow-up.

5.1.1 Visit schedule adjustments due to infection precautions:

If circumstances arise where individuals cannot attend assessment visits in-person (e.g. due to system-wide precautions related to infection control), participants will engage in screening and assessment procedures remotely as applicable. Participants electing to participate in Stage 2 of the assessment process will then be invited at a later date to return on site to complete in-person assessment visits as timing and infection control procedures permit.

Figure 1: Study Flow

5.2 Screening phase

We will screen individuals either at the point of care or by telephone. Screening may also occur online via Redcap with a follow-up telephone call from study personnel. Following screening, we will schedule

eligible participants for a study enrollment visit to undergo consenting procedures and a one or two-stage clinical assessment (1) psychological measures online, and 2) in person psychophysical measures, and biological samples). Participants will then be randomized to an 8-week intervention or control condition. See Screening (section 4.2) for more information.

5.3 Randomization procedures

Patients will be randomized to the psychosocial self-management group (SM) or attentional control (AC) group after their first assessment visit. Randomization will occur at a 2:1 rate favoring our treatment condition, which will increase power in planned subgroup analyses. Randomization will be unblinded and occur through stratified permuted block methods using randomly-assigned variable blocks (2, 4, and 6). Participants will be stratified by opioid use levels, with those who take opioids more than 3 days per week defined as “regularly using opioids.” Randomization will occur following participants’ study enrollment visit and online assessment completion (Stage 1 assessment) to avoid any selection bias and to ensure adequate balance between treatment groups throughout the study accrual period. These procedures will be conducted by a study biostatistician so that the blocking factor is not known to the study PI or enrollment team to guard against any further selection bias.

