3. SPECIFIC AIMS

Aim 1: To construct a patient-centered CBT self-management (SM) intervention specific to IC/BPS. We will construct a self-management intervention for IC/BPS with information compiled from patient focus groups (preliminary data), clinical expertise, and effective components of self-management interventions in associated conditions. We will work in collaboration with IC/BPS experts and utilize research collected from an ongoing project (MAPP) to inform intervention design. We will then invite focus group participants to return and review the intervention package for acceptability.

Aim 2: To obtain pilot data comparing the effectiveness of integrating SM interventions into standard care (N = 50) to attention control (AC, N = 25) in improving targeted genitourinary symptoms (GUPI,⁴ primary outcome) and secondary outcomes of pain, distress, and quality of life. We hypothesize that individuals receiving the SM intervention will show improved outcomes relative to control [AC].

Aim 3: To determine whether patient phenotype moderates treatment response to a SM intervention. We will define patient phenotype by: assessment of temporal summation (as a marker of central sensitization), degree of psychological co-morbidities, and presence of chronic overlapping pain conditions. We hypothesize that (1) higher levels of pre-treatment psychological co-morbidities (e.g. depression levels) will be associated with greater SM treatment efficacy, (2) we hypothesize that greater baseline temporal summation will be associated with greater SM treatment efficacy, and (3) we hypothesize that participants with more chronic overlapping pain conditions will exhibit greater SM treatment efficacy.

Successful completion of these aims will determine whether the addition of a tailored self-management intervention for IC/BPS will improve patient symptoms and function, whether particular patient

subgroups are more responsive to this intervention, and whether a potential biological mechanism (central sensitization) influences treatment responsiveness. We summarize these aims in the table below.

	Summary	Hypothesis
Aim 1	To construct a patient-centered CBT self-management (SM) intervention specific to IC/BPS.	N/A

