1. For those patients with Do Not Contact for their research contact preference, we propose to contact their providers to request that they connect with the patient about this study opportunity, should they deem it appropriate. We will provide them with a recruitment message, once again including access to our REDCap Interest Form, to distribute to patients accordingly. [name] has extensive connections to providers through the IC Clinic and throughout VUMC, many of whom have expressed enthusiastic interest about aiding in recruitment efforts.
2. For those patients with Ok to Contact for their research contact preference, we propose direct-messaging, in eStar or via email, these patients with a recruitment message that includes a link to our IRB-approved Interest Form. In eStar, these patients will be sent our direct recruitment message up to two times. From there they can either reply to our message, contact our study team,

or fill out our REDCap form. Per our recruitment procedures, we will give them a final phone screening if they indicate interest.

This condition is greatly understudied and needs more research, as patients subjectively report that even diagnosis alone can take years of ruling out alternative conditions. We also have excellent rates of study enrollment and retention in our first year. Thus, providers and participants alike have largely been overwhelmingly positive about this study. We believe that our goal of $n = 75$ is in reach and could be helped greatly by incorporation of these EHR-based recruitment options.

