5.4 Enrollment

We propose to enroll 96 participants in order to ensure complete data from 75 participants, assuming a very conservative 30% drop-out rate. We will monitor the dropout rate on an ongoing basis, and modify the number of participants recruited as needed to ensure a final sample of N = 75 study completers.

The study will enroll up to a total of 96 consecutive adults (aged \geq 18 years) with IC/BPS to participate in baseline and follow-up clinical assessment and quantitative sensory testing. Eligible participants will be randomized to an intervention (cognitive-behavioral self-management) or active control condition at a 2:1 rate. Following randomization, $\frac{2}{3}$ of participants will be provided with a cognitive-behavioral self-management intervention, and the other $\frac{1}{3}$ will engage in an active attention control condition. Those enrolled in the study will also be followed after the intervention time period of 8 weeks and again at 3 months.

The registration process will occur through VUMC either at the Osher Center for Integrative Medicine at Vanderbilt, located at [REDACTED], [name], online, or at the VUMC Clinical Research Center at [REDACTED], [name]. All participants will have a VUMC medical record identification number prior to beginning the study. Consenting will occur in-person or remotely where questions can be answered by a member of the research team, and assessment measures will be completed electronically on-site at VUMC or remotely online through a secure RedCap link. Consenting procedures will occur electronically in eConsent format online or on site using an electronic device where participants can fill out study measures online through RedCap. Psychophysical and Quantitative Sensory Testing will occur at the same site. After participants enroll in the study and complete their pre-treatment assessment, they will be randomized to the treatment or control condition.

For aims 2 and 3, we anticipate enrolling our first patient in the second half of the study’s first year. Given our recruitment strategies, we anticipate consistent enrollment of subjects in years 1 (N=10), 2 (N=43), 3 (N=43) of the project, peaking in years 2 and 3. We aim to reserve the majority of year 4 to conclude data collection and focus on data analysis, manuscript preparation, and additional grant

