9. STATISTICAL CONSIDERATIONS

9.1 Analytic Plan by Aim

Aim 1: To construct a patient-centered CBT self-management (SM) intervention specific to IC/BPS. Pre-work for this aim will include a theme analysis of coded transcripts from focus groups using NVivo 9 to code, analyze, and interpret transcripts using elements of grounded theory.⁷⁸ For the project period, this aim will primarily involve consolidating qualitative work and will use descriptive statistics where appropriate.

Aim 2: To obtain preliminary data comparing the effectiveness of integrating SM interventions into usual treatment (N = 50) to control (AC, N = 25) in improving targeted primary (symptom improvement [≥ 7 point reduction in GUPI]) and secondary (pain, distress, quality of life) outcomes.

Power and sample size considerations: ■ are comparing GUPI-Total Score, a continuous variable, between the SM group and a matched AC group with a 2:1 randomization scheme. The GUPI-Total Score tends to be normally distributed with a standard deviation of 8.61.^{47,79} A 7-point decrease in total GUPI score is considered clinically meaningful⁷⁹ and a robust assessment of response to treatment.⁴

Assuming a Type I error of 0.05 and power of .90, we will need 50 experimental subjects and 25 control subjects to reject the null hypothesis that the sample means of both treatment groups are equal post-treatment. ■ intend to have 50 experimental and 25 control subjects to obtain even groups for analytical purposes, as recommended by ■ DSBM. Given our use of statistical models, ■ power is increased when ■ appropriately adjust for covariates.

■ will test the hypothesis that those receiving the SM intervention will show improved outcomes relative to AC. ■ will use generalized linear mixed models to compare responses on the Genitourinary Pain Index (GUPI⁸⁰-Primary Outcome) between treatment groups, adjusting for baseline GUPI and covariates. As recent evidence recommends the examination of pain and urinary symptoms separately,²⁵ ■ will examine the GUPI pain subscale and GUPI urinary subscale separately in secondary analyses. ■ will perform one interim analysis at approximately 50% completion of data collection using the O'Brien-Fleming method to preserve alpha accounting for repeat testing.

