■ will examine changes in secondary outcomes of interest, including pre- to post-treatment changes in emotional distress (e.g. PHQ-8, GAD-7, PCL-5, CSQ), quality of life and wellness (e.g. PROMIS-29), widespread pain (MBM/Choir bodymap), and perceived treatment benefit (PGI) using similar approaches: linear models for continuous outcomes, proportional odds models for ordinal outcomes, and logistic models for binary outcomes. As ■ training in data analysis progresses, ■ will apply more sophisticated approaches, such as hierarchical modeling. As ■ anticipate potential confounding from factors such as age and time since diagnosis, we will account for these as covariates in the analyses. Further, as opiate use is associated with increased pain sensitivity and decreased pain thresholds on psychophysical testing,⁷³ ■ will stratify groups by opiate use during randomization. ■ will additionally consider opiate use as a covariate in the analyses. To address sex as biologic variable, we will examine sex as a moderator of treatment effects, since men and women perceive pain differently in self-report⁷⁴ and sensory testing.⁸¹

Aim 3: To determine whether patient phenotype moderates treatment response to a SM intervention. As an exploratory aim, ■ will assess the hypotheses that a) higher pre-treatment psychological distress, b) higher baseline temporal summation, and c) number of chronic overlapping pain conditions will be associated with greater SM treatment efficacy. To avoid loss of power from testing a phenotype x treatment x time interaction, ■ will model the change in GUPI and treatment response (PGI) using a proportional odds model adjusted for baseline GUPI, and test for a treatment x phenotype interaction. A positive finding would suggest treatment effects depend on these moderating factors. ■ increased our sample size for this analysis by applying a 2:1 randomization scheme; however, given that our treatment group still constitutes a small sample size (n=50), ■ will set a threshold of p<.2 for the interaction before proceeding with a responder or mediation analysis. ■ will use these analyses to identify factors needing consideration in future studies expanding the generalizability of SM.

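### Section 5.3 sets 2:1 allocation but lists permuted blocks of 2, 4 and 6; sizes 2 and 4 cannot hold 2:1, so the written rule does not assure the planned split

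*Combined protocol and SAP*

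**What the plan says.** Section 5.3 (Randomization procedures) first fixes the ratio: "Randomization will occur at a 2:1 rate favoring our treatment condition". The next sentence fixes the method: "Randomization will be unblinded and occur through stratified permuted block methods using randomly-assigned variable blocks (2, 4, and 6". Allocation is stratified by opioid use, with regular use defined as more than 3 days per week. A study biostatistician runs the procedure "so that the blocking factor is not known to the study PI or enrollment team".

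The ratio is consistent elsewhere:

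- Section 3, Aim 2: "integrating SM interventions into standard care (N = 50) to attention control (AC, N = 25".
- Section 5.4: "Eligible participants will be randomized to an intervention (cognitive-behavioral self-management) or active control condition at a 2:1 rate", followed by a split of two thirds and one third.
- Section 9.1, Aim 2: the comparison is "between the SM group and a matched AC group with a 2:1 randomization scheme", with 50 and 25 subjects for 90% power.
- Section 9.1, Aim 3: the interaction threshold is relaxed "given that our treatment group still constitutes a small sample size (n=50".

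No section says how a block of 2 or 4 is filled, or that 2, 4 and 6 multiply a smaller unit. Section 4.1 indicates that recruitment has begun: "We also have excellent rates of study enrollment and retention in our first year".

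**The concern.** The two adjacent sentences of section 5.3 do not fit together. The intended ratio is clear, and the block sizes are what conflict with it. Anyone who builds, checks or reports the list from this text has to guess how two of the three block sizes are filled.

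Three things depend on that guess: the overall SM:AC split, the 50 SM completers quoted for Aim 3, and an accurate account of allocation in the CONSORT report promised in section 4.1. Depending on the fill, the trial could have too few SM patients for its stated plan, or too few controls for its stated power.

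**Working it through.** **Inputs.** Ratio 2:1 and block sizes 2, 4, 6 (section 5.3); 96 enrolled and 75 completers (section 5.4); 50:25, SD 8.61, 7 points, alpha 0.05 and power 0.90 (section 9.1). Assumptions: the test is two-sided (not stated), 7 points is the between-group difference, the three sizes are equally likely, and dropout is equal by arm.

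**1. The plan's own sample size.** Standardised difference: 7/8.61 = 0.813. Normal approximation for AC under 2:1: (1 + 1/2) × (1.960 + 1.282)² / 0.813² = 1.5 × 10.51 / 0.661 = 23.9, so 24 AC and 48 SM. The two-sample t-test (noncentral t) gives power 0.894 at 48:24 and 0.906 at 50:25. So 50:25 is the smallest exact 2:1 split with at least 90% power, and the plan's figure reproduces.

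**2. Which blocks can hold 2:1.** A block of size b needs 2b/3 SM and b/3 AC, both whole numbers.

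- b = 2: 1.33 and 0.67, not possible.
- b = 4: 2.67 and 1.33, not possible.
- b = 6: 4 and 2, possible.

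**3. What the split becomes.** One block of each size holds 2 + 4 + 6 = 12 places. The expected SM share is the number of SM places divided by 12. The intended number among 96 is 96 × 2/3 = 64; this is derived, since the documents print only 50:25. The 95% ranges come from 5,000 simulated lists per fill, with two strata and 30% regular opioid users assumed.

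| Fill of blocks 2, 4, 6 (SM:AC) | SM share | SM of 96 (95% range) | Split of 75 | Power |
|---|---|---|---|---|
| 1:1, 2:2, 3:3 | 6/12 = 50.0% | 48 (47–49) | 38:37 | 0.935 |
| 1:1, 2:2, 4:2 | 7/12 = 58.3% | 56 (52–59) | 44:31 | 0.928 |
| 1:1, 3:1, 4:2 | 8/12 = 66.7% | 64 (61–67) | 50:25 | 0.906 |
| 2:0, 3:1, 4:2 | 9/12 = 75.0% | 72 (68–76) | 56:19 | 0.856 |

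The split of 75 is the share times 75 (37.5, 43.75, 50 and 56.25), rounded. Power is the two-sided t-test at that split, for difference 7 and SD 8.61.

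**4. Comparison with blocks that are multiples of 3.** Sizes 3, 6 and 9 at exact 2:1 give 64 of 96 (63–65). If 2, 4 and 6 were multipliers of a unit of 3, the sizes 6, 12 and 18 would give 64 (62–66).

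**5. Aim 3.** With equal moderator spread in both arms, the variance of the treatment-by-phenotype interaction scales with 1/n(SM) + 1/n(AC). This is 0.0533 at 38:37, 0.0550 at 44:31, 0.0600 at 50:25 and 1/56 + 1/19 = 0.0705 at 56:19. Drift towards 1:1 does not cost precision in that test. Over-allocation to SM does.

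**The case against.** The strongest reply is that 2, 4 and 6 may be multipliers of a base block of 3, in which case the list carries 2:1 and only the wording is wrong. That is possible, and the fix allows for it. But section 5.3 calls the numbers blocks and mentions no base unit.

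A second reply is that the protocol promises a 2:1 rate overall and does not require 2:1 inside every block. That is correct. The third fill above averages 2:1, so it would be too strong to say that the rule cannot be carried out. But no such fill is specified, so 2:1 is not assured.

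A third reply is that the consequence is small because power does not suffer. This holds for the fills that average 2:1 or drift towards 1:1. It does not hold for the fill that gives SM the surplus places, which the text does not exclude.

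A reader might also infer that patients were in fact allocated 1:1, that the sizes are left over from an earlier 1:1 design, or that the comparison is biased. The documents support none of these. The list is not shown, no earlier design is described, and a wrong ratio in a properly generated random list is not in itself a source of bias.

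**Conclusion.** Section 5.3 is wrong as written: two of its three block sizes cannot carry the ratio it states, and nothing else in the documents resolves this. The finding concerns the written rule, not what was done.

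Under equally likely block sizes and equal dropout, the expected SM count ranges from 48 to 72 of 96 over the four fills shown, against 64 intended. These are scenarios, not predictions. Power stays above 0.90 unless the list over-allocates to SM, where it is 0.856 at 56:19. Neither a general loss of power nor a general assurance that power is safe can be drawn from the text. The point should be corrected because allocation is a core element of the design and the check is cheap.

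**What to change.** 1. The study biostatistician checks the list in use: the block sizes, how each was filled, and the realised SM:AC ratio in each opioid stratum.
2. If the list carries 2:1 (for example, if 2, 4 and 6 multiply a base block of 3), correct the sizes in section 5.3 to multiples of 3. Alternatively, say that block sizes vary at random, each a multiple of 3 and holding SM to AC at 2:1, and keep the exact sizes in a restricted document. The second wording suits the aim of keeping the blocking factor from the enrolling team. If the list reaches 2:1 only on average through an uneven fill, that sentence would misdescribe it, and section 5.3 should state the fill used.
3. If the list does not carry 2:1, generate the remaining allocations within each opioid stratum in blocks that are multiples of 3, such as 3, 6 and 9. Section 5.3 should then describe both the earlier and the later rule, with the date and the number randomised at the change. Add allocation period as a covariate in the primary model, because the ratio would differ by calendar time. A time trend is plausible: recruitment runs over about three years, and section 5.6.1.1 allows delivery to move online.
4. Report the realised ratio overall and by stratum. Restate the 50:25 and 90% power figures if the realised split differs.

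Cost: one list check and a text correction, with no extra patients. If the list must change, add a documented mid-trial amendment, notice to the DSMB (section 9.1 cites its recommendation for the group sizes) and one covariate. Even then the overall split may not reach 2:1. For example, 48 patients at 1:1 followed by 48 at 2:1 gives 24 + 32 = 56 SM of 96, or 58%.

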5.6.3 Fidelity monitoring

The PI will oversee intervention training and delivery by adhering to NIH Behavioral Change Consortium guidelines⁴² recently reviewed as applied to clinical pain trials in Edmond (2018).⁴³ This will include structured training in intervention delivery, recording of sessions, and the PI engaging in weekly supervision with trial therapists to review content summary guide checklists and session material.

Clinical assessments

The battery of assessments below will be given at pretreatment, posttreatment, and at the three-month follow-up mark. Assessments will be completed in two stages at each timepoint: 1) online patient reported outcome measures and 2) in person psychophysiological testing and the collection of biological samples.

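### Section 5.3 says the blocking factor is hidden from the PI and enrollment team but prints the block sizes (2, 4, 6), so the concealment safeguard is only partial; the gain to a guesser at 2:1 is modest (minor)

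*Combined protocol and SAP*

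**What the plan says.** All from the Combined protocol and SAP.

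- **Section 5.3, method:** "Randomization will be unblinded and occur through stratified permuted block methods using randomly-assigned variable blocks (2, 4, and 6". The sizes are printed in full.
- **Section 5.3, ratio and strata:** "Randomization will occur at a 2:1 rate favoring our treatment condition", and "Participants will be stratified by opioid use levels". There is one stratifier with two levels.
- **Section 5.3, safeguard:** the biostatistician runs the procedure "so that the blocking factor is not known to the study PI or enrollment team to guard against any further selection bias". Allocation follows the enrollment visit and the Stage 1 online assessment.
- **Section 5.6.3:** fidelity monitoring includes "the PI engaging in weekly supervision with trial therapists to review content summary guide checklists and session material". Section 6.6 adds that the PI reviews session recordings.
- **Section 4.2:** interested candidates who meet the inclusion criteria "will be contacted by the PI or a member of the research team (e.g. research coordinator, post-doctoral fellow, or research assistant". The telephone script (Appendix B) sends unclear screening answers to the PI.
- **Section 5.1, at the enrollment visit and before allocation:** "The eligibility checklist will be reviewed again to ensure participants meet criteria and assessment battery will be given".
- **Section 4.4, items 8 and 9:** interfering life events and major medical issues are exclusions that need judgement.

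No other concealment step is described.

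**The concern.** The safeguard is meant to keep the people who decide on entry from anticipating the next arm. Anyone who works from this protocol has the sizes, the ratio and the stratifier. The PI, whom the safeguard names, also has a documented route to past assignments and a part in candidate contact and in unclear screening decisions.

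If the next assignment is partly predictable, whether or when a borderline candidate enters could depend, even unconsciously, on the expected arm. That would bias the comparison of SM with attention control (AC) on the GUPI, a self-reported primary outcome. Adjusting for baseline GUPI removes only the part of such selection that baseline GUPI captures. The protocol would also be claiming more concealment than its text provides.

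**Working it through.** The plan states no guessing probability, so there is no figure to reproduce.

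**1. What 2:1 implies for the printed sizes.** SM places per block = size × 2/3.

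- Size 2: 1.33
- Size 4: 2.67
- Size 6: 4

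Only 6 carries 2:1 exactly, so a reading must be assumed. The closest is SM:AC of 1:1, 3:1 and 4:2. Drawn equally often, these give 8:4 = 2:1 overall.

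**2. Baseline.** At 2:1, always guessing SM is right 2/3 = 66.7% of the time.

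**3. Gain from knowing the sizes.** I simulated sequences within strata. The guesser knows the set of sizes and all past assignments in the stratum, does not know the current size, updates by Bayes' rule and picks the more probable arm. Equal size probabilities are an assumption.

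| Sizes | Correct | Certain | Known at ≥90% |
|---|---|---|---|
| 2/4/6 rounded toward 2:1 | 72% | 3% | 17% |
| 2/4/6 read as multipliers (6/12/18) | 70% | 2% | 6% |
| 3/6 | 75% | 10% | 34% |
| 6/9/12 | 72% | 2% | 8% |

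Results were nearly the same with 10% or 30% regular opioid users (shares assumed).

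**4. Which arm is predictable (2/4/6 rounded).** The 17% splits into about 16.4% SM and 0.4% AC. When the guesser predicts AC, AC follows about 66% of the time, against a base rate of 33%.

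**5. From predictability to bias.** Let f = P(SM expected | assigned SM) − P(SM expected | assigned AC), with slots that favour neither arm counted as half. Then bias = f × gap, where the gap is the difference in prognosis between patients entered when SM is expected and those entered when AC is expected. For 2/4/6 rounded:

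- most-probable-arm rule: f ≈ 0.25
- rule that calls a slot SM or AC according to whether its SM probability is above or below 2/3, ties neutral: f ≈ 0.355

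**6. Effect on the test.** SE = 8.61 × √(1/50 + 1/25) = 2.11, using the SD and group sizes in section 9.1. Two-sided error = Φ(−1.96 + bias/SE) + Φ(−1.96 − bias/SE). The gap of 2 to 3.5 GUPI points is assumed.

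| f | Gap | Bias | Error |
|---|---|---|---|
| 0.25 | 2 | 0.50 | 5.6% |
| 0.25 | 3.5 | 0.875 | 7.0% |
| 0.355 | 2 | 0.71 | 6.3% |
| 0.355 | 3.5 | 1.24 | 9.1% |
| any | 0 | 0 | 5.0% |

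**The case against.** The case against making much of this is strong, and most of it stands.

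- **A reader might infer that the next assignment can be guessed well above chance.** The documents do not support that. A gain of about 20 points (70% against 50%) appears only if the blocks are filled 1:1, which contradicts the 2:1 ratio in sections 5.3 and 5.4. At 2:1 the gain is about 3 to 5 points.
- **The share known with high probability is almost all SM.** AC, the rarer arm, is almost never known with confidence.
- **The order of the sizes is random and not printed.** The blocking factor could fairly mean the current block size, which does stay hidden. Printing three small sizes still weakens the safeguard.
- **Other protections exist.** Allocation follows consent and Stage 1. Section 5.4 describes consecutive enrollment, section 4.3 a structured checklist, and section 4.1 records of exclusion reasons. These narrow the room for steering but leave some discretion over timing and over exclusion items 8 and 9.
- **Access to past assignments is documented for the PI only.** For the enrollment team it would be inference.
- **Larger blocks alone change little.** For 6/9/12, accuracy is still about 72% and f is 0.26 or 0.33 by the two rules. Only the share known at ≥90% falls, from 17% to 8%.

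What survives is the conflict within section 5.3 and the absence of a stated step that separates the eligibility decision from knowledge of the sequence.

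**Conclusion.** The point holds as a minor one. Section 5.3 claims that the blocking is concealed and discloses the set of sizes in the same paragraph, in a trial whose PI can see past assignments, so the safeguard is partial.

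At the documented ratio the advantage over always guessing SM is about 5 points (about 3 if the printed numbers are multipliers). It is more noticeable for AC predictions, which come true about twice as often as the base rate. The error range of 5.6% to 9.1% depends on an assumed gap and on the guessing rule. It illustrates what steering could do and is not an estimate for this trial. Nothing in the documents shows that steering occurs, and without it the error stays at 5%. The simulation also assumes equally likely sizes and the rounded reading of 2, 4 and 6.

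**What to change.** In section 5.3, replace the printed sizes with: *randomly varying block sizes compatible with 2:1, held only in a restricted randomization document kept by the study biostatistician.* Add two statements:

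- eligibility is locked in REDCap before the assignment is requested;
- arm tallies by stratum are not circulated to staff who confirm eligibility.

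These two statements matter most, since changing the sizes alone does little.

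The 2:1 ratio requires multiples of 3 in any case. When the sizes are corrected, avoid 3/6, which is more predictable than the rounded current set (75% guessed correctly, 34% known at ≥90%). Prefer larger multiples such as 6/9/12 (72% and 8%). The gain in concealment would not by itself justify a fresh list for remaining participants.

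The cost is a short amendment using the existing biostatistician and REDCap. The one downside is slightly more possible imbalance between arms within the smaller opioid stratum.
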